Based on the above hypothesis this study will be considered successful in demonstrating superior efficacy relative to control if consumption of opioids postoperative is significantly less among patients randomized to receive a

continuous TAP block via the ON-Q[®] system compared to the patients randomized to receive a single TAP injection of Exparel (liposomal bupivacaine) or single TAP injection of Ropivacaine to treat postoperative pain. However, a finding of no difference between the continuous catheter technique and the Exparel arm would also be considered beneficial to the advancement of post-operative pain control techniques because it would demonstrate similar post-operative pain control can be achieved without the extra time and skill required to place a catheter.

Statistical Methods

Sample Size

The main objective of study is to compare total opioid consumption between the single shot TAP group and the Exparel TAP group with a parallel design. Based on previous studies and internal pilots, the mean total opioid consumption (standard deviation) was 4.1 mg (SD 3 mg) in single shot group and 2.4 mg (SD 1.3 mg) in Exparel TAP group. For the sample size calculation, a standard deviation of 3 is used as a conservative estimate. To detect a difference in mean opioid consumption between treatment groups, 4.1 mg vs. 2.4 mg, a sample size of 49 patients per arm is required to achieve 80% power with a significance level of 0.05 using a two-sided t-test or Wilcoxon rank-sum test depending on normality test. A secondary aim is to examine a difference in mean opioid consumption between the single shot TAP group and continuous TAP group. Allowing for a 10% dropout rate, a total of 159 participants with 53 participants in each arm will therefore need to be recruited into the study. It anticipated that approximately 8 participants per week will be enrolled into this study, thus the estimated accrual time is around 1 year.

Statistical Analysis Plan

All analyses will be conducted on patients following an intention-to-treat principle, including all randomized participants enrolled in three arms, in case of relevant non-compliance to the treatment and/or impossibility to evaluate the endpoints, a per-protocol analysis will also be performed, together with an analysis of non-compliance/non-evaluation.

Patient characteristics and outcomes data will be summarized by cross-tabulation (categorical variables), quartiles (median, ordinal variables), and mean and standard deviation (continuous variables). Comparisons between groups will use Chi-square test or Fisher's exact test as appropriate for categorical variables and t-test or Wilcoxon rank-sum test as appropriate for continuous variables.

Analyses of primary outcome will examine differences in mean opioid consumption between the single shot TAP group and the Exparel TAP group. Analyses of secondary outcomes will examine differences in mean opioid consumption between the single shot TAP group and continuous TAP group. Treatment groups will be compared using a

student's t-test if data are normal distributed or Wilcoxon rank-sum test if not normal distributed.

The differences in mean opioid consumption across three groups (single shot TAP, continuous TAP, and Exparel TAP) will be examined with a test of means between groups using one-way analysis of variance (ANOVA). A comparison between continuous TAP and Exparel TAP will be performed. A t-test will be used if the observations in each trial arm are normally distributed; if non-normally distributed, then rank-based methods such as Wilcoxon rank-sum test will be employed.

All tests will be two-sided.

The overall incidence of serious adverse events and adverse events and number and proportion of patients reporting such events will be summarized by treatment group. Adverse events will be tabulated and summarized by the number and percentage of subjects who experienced the event.

Missing Outcome Data

Analysis will be conducted as described in prior section. Missing data will not be included in the analysis; however, may lead to an increase in patients recruited into one or more study arms.

Unblinding Procedures

This study is not blinded because it will be obvious to all care givers whether or not the patient received a continuous block with catheters or not.

H Data Handling and Record Keeping

Confidentiality and Security

Data will be collected on the data collection forms located in Attachment L9 and entered into the Oncore ERM study management system.

Data collection forms will be stored at each respective study site within a locked cabinet in a locked research office.

The Oncore ERM study management system is a secure web-based management system that is password-protected. Access to data is role-specific.

All study sites will observe Health Insurance Portability and Accountability Act (HIPAA) Privacy and Security Rule standards.

Training

All research team members must complete approved Human Subjects and HIPAA training.

All research team members must complete Oncore ERM training.

Case Report Forms and Source Documents

Study sites will utilize the data collection forms in Attachment L9 to collect data and will enter data into the Oncore ERM study management system.

Records Retention

Paper study records will be maintained at the respective study sites for seven years from the end date of the study. At the end of this time period, study records will be shredded.

Data in the Oncore ERM study management system will be stored for seven years from the end date of the study. At the end of this time period, records will be deleted.

Performance Monitoring

The IRB and the Principal Investigator will monitor study performance using the Oncore ERM study management system.

I Study Monitoring, Auditing, and Inspecting

Study Monitoring Plan

The IRB and the Principal Investigator will monitor ongoing study performance using the Oncore ERM study management system.

Auditing and Inspecting

The IRB will audit and inspect study materials at the study sites as indicated.

J Study Administration

Organization and Participating Centers

The Principal Investigator at the lead institution will collaborate with study site Principal Investigators to oversee this study.

Funding Source and Conflicts of Interest

There are no conflicts of interest among any of the study investigators.

Study investigators must complete institution-specific conflict of interest forms as required.

Subject Stipends or Payments

Subjects will not be paid for their participation in the study.

Study Timetable

The study will last for approximately four months. This is the estimated time based on current operating room patient criteria to enroll ninety patients into the study.

κ Publication Plan

Upon completion of study and statistical methods, it would be expected to publish the study in an established and well-read peer journal of either Anesthesiology or Surgery. Given that an analysis demonstrating a statistically significant difference or no difference between any of the study arms would be useful to how anesthesiologist and/or the surgical team approach the TAP block, it is highly likely the study would be accepted for publication.

L Attachments – TAP Block Pain Management Data Form

Schedule of Measurements Template (add additional information as needed)

Anesthesiologist performing TAP BLOCK	Surgeon
Date of Surgery	Hospital Discharge Date
Procedure  Ventral hernia  Expl. Lap  Colon  Small Bowel  Anterior Resection  APR  Lower Anterior Resection  Prostate  TAH  HIPEC  Cyto-reductive Surgery  Ileostomy reversal  Robotic Assisted +/- Hand Assisted  Robotic (no incision)  L/S Assisted +/- Hand Assisted  L/S (no incision)  Other _____	 Continuous TAP with Ropiv 0.2%  Single Shot TAP  Exparel  0.25% Bupivacaine  Pre-incision  Post-incision Other: _____

PATIENT INFORMATION

Initials	Outpatient / SDA  Patient taking narcotics at home prior to surgery?  Yes  No	Inpatient (prior to Surgery)  PCA  IV narcotics  (skip if PCA) P.O. Narcotics  (skip if PCA)	
Age	Gender  M  F	Race  Cauc  Black (Non Hisp)  Hisp  Asian  Other	ASA
BMI	Smoking  Yes  No	Diabetes  Yes  No	
Incisional Dermatone Level Range: (Umb=T10)	Surgery Duration (minutes)	PACU Time until nurse gives report	

Outcomes	PACU	POD 0	POD 1	POD 2	POD 3
PCA		 Y  N	 Y  N	 Y  N	 Y  N
NARCOTICS					
MSO4 (mg) total requirements					
Dilaudid (mg) total requirements					
Fentanyl (mg) total requirements					
Anti-emetic Given (+/-)					
EVENTS					
Bowel Movement (+/-) (record 1 st day only)					

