Although, there is a fair amount of literature and case reports for TAP block for post-op pain; there is very little data that goes out as far as 72 hrs. Furthermore, those studies (albeit limited) demonstrate a difference that is not considered statistically significant between single shot TAP block and controls that did not receive TAP block at 72 hrs. Studies do however show a statistically significant difference in narcotic requirements and pain scores at 24 hrs (post-operative day [POD] #1), and at 48hrs (POD #2) between single shot TAP and placebo^{4,12} and also between continuous TAP techniques and placebo¹³. However, no direct comparison study exists between continuous TAP Block techniques and standard single shot Bupivacaine technique. Using prior studies as a reference and making the appropriate equianalgesic conversions to account for the difference in narcotic potencies used in the various studies we can come to the expectation that total hydromorphone (Dilaudid) requirements would be roughly 50% lower in the continuous catheter TAP technique vs. the standard single shot Bupivacaine TAP technique at 48hrs. We estimate total Hydromorphone requirements over 48 hrs. in the control (single shot TAP) to be equal to 4.1mg versus the continuous catheter TAP group equaling 2.4 mg. We would also assume Exparel TAP to be equal to catheter TAP at 2.4 mg. Furthermore, Visual Analog Scales as expected follow a similar trend, with the most significant difference seen at 48 hrs.^{4,11-13}

Rationale for this Study

The rationale for this study is to examine the post-operative pain benefits of continuous release TAP techniques (Catheter technique and liposomal slow release Exparel® technique) versus the

standard single shot Bupivacaine injection for TAP block. Therefore, in this study the standard single shot Bupivacaine technique acts as the control.

Although both modalities of continuous release TAP block have been proven versus placebo to provide post-operative pain relief over an extended time period; there is no such study that directly compares the standard single shot Bupivacaine technique to the continuous release TAP techniques in terms of quality or ability to control post-operative pain. Given the significant increased cost along with in the case of the catheter group skill, procedural time, and maintenance management there should be a significant improvement in post-operative pain duration versus the single shot Bupivacaine TAP block technique.

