
Furthermore, our expectation is that this difference will be most apparent at 48 hrs. as discussed above with a reduction in narcotic requirements greater than 40% in the continuous catheter TAP group vs. standard single shot Bupivacaine TAP (4.1 mg +/- 3 mg vs. 2.4 mg +/- 1.3 mg Dilaudid). This is based on the assumption that the effects of the local anesthetic control TAP (single shot Bupivacaine) may last up to 24 hrs. At 72 hrs, prior studies, although limited, have not shown a significant difference between TAP block and placebo groups.

c Study Objectives

Primary Aim

The primary aim is to evaluate for any significant difference total post-operative narcotic requirements (Dilaudid) required over 48 hrs. in the continuous catheter TAP block arm vs. the single shot Bupivacaine TAP arm and again the slow release Liposomal Exparel® TAP arm vs. the single shot Bupivacaine TAP arm.

Secondary Aim

The secondary aim will be to evaluate for any significant difference in narcotic requirements at other endpoints such as 24 hrs and at 72 hrs. As discussed before, current studies do not show a significant difference when extrapolated out at those end points, albeit there is very little data at 72 hrs. Other quality indicators of recovery in the three arms such as Visual Analog Scores (VAS) are expected again to be most significantly different at 48 hrs. Other quality measures that will be recorded include incidence and severity of post-operative nausea and vomiting (PONV), time to ambulation, and patient satisfaction with post-operative pain control.

Rationale for the Selection of Outcome Measures

Outcome measurements are based on the assumption that narcotic requirements (i.e. intravenous Dilaudid Patient-Controlled Analgesia [PCA] use) are inversely related to patient satisfaction in regards to their post-operative pain. Additional factors such as VAS, ambulation, performance of daily activities, and anti-emetic pharmaceutical requirements have been chosen as quality indicators in regards to post-operative pain control and dependence on narcotics.

D Investigational Agent

This investigation will use three FDA-approved techniques:

- Bilateral Continuous TAP block via Catheter (One-time bolus of Bupivacaine 0.25% x 20ml per side followed by continuous infusion of Ropivacaine 0.2% 7 ml/hr. per side x 48 hrs.);
- Single Injection TAP block with Exparel® (One-time bolus of Bupivacaine 0.25% x 20 ml followed by Exparel 133 mg per side); and

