will be flushed with the Bupivacaine syringe. 2) The TAP space will be located using the Bupivacaine syringe under ultrasound guidance. 3) Once the TAP space, Exparel 133mg will be injected into the TAP space. 4.) After injection, the syringe will be exchanged for the Bupivacaine syringe and the residual Bupivacaine will be injected into the space (~20ml). Steps 2-4 will be repeated for the opposite side TAP block.

- 3) Continuous Catheter Arm: A total of 40 ml Bupivacaine 0.25% vials will be pre-drawn up via two 20 ml Syringes. The Bupivacaine 20ml syringe will be connected to IV tubing. The distal end of the IV connection will be maintained sterile and will be connected to the injection touhy needle. Procedure step 1) The entire setup will be flushed with the Bupivacaine syringe. 2) The TAP space will be located using the Bupivacaine syringe and ultrasound guidance. 3) Once in the TAP space, 5-10ml Bupivacaine 0.25% will be injected into the TAP space. The IV extension will then be disconnected from the touhy needle and a catheter will then be threaded via the touhy needle and into the TAP space. The proximal end of the catheter will then be connected to the distal end of the IV extension set and the residual Bupivacaine 0.25% from the 20ml syringe will then be injected thru the catheter. The catheter will then be secured and dressed via standard technique for catheter placement. Steps 2-4 will then be repeated for the opposite side TAP block. In the PACU, patients will receive a pre-filled ON-Q[®] system obtained through the hospital pharmaceutical department. The pre-filled ON-Q[®] system contains Ropivacaine 0.2% in a 700 ml container. The infusion pump will be set to run at a rate of 7 ml/hr. per side.

Breakthrough pain will be managed similarly in all three arms via Dilaudid IV PCA every 10 minutes with clinician bolus function of 0.5 mg every 30 minutes.

E3.d Subject Compliance Monitoring

The Principal Investigator will oversee compliance with study procedures.

E3.e Prior and Concomitant Therapy

N/A

E3.f Packaging/Labeling

N/A

E3.g Blinding of Study Drug

It will be impossible to blind the catheter group from practitioners and floor care nurses given the obvious appearance of the catheters. However, the floor care nursing and staff will be blinded between the single injection arms: Exparel and Ropivacaine. The

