F3.d Data Collection Procedures for Adverse Events

Please see Attachment L2 for data collection form. All adverse event data will be entered into Oncore ERM.

F3.e Reporting Procedures

Serious Adverse Events and adverse events that meet "severe" criteria must be directly reported within 24 hours to the Principal Investigator, and the IRB.

[name] M.D.
[contact]
[contact]
Department of Anesthesiology
Midwestern Regional Medical Center
Zion, IL

Other adverse events must be entered within 7 days of collection into the Oncore ERM.

F3.f Post-study Adverse Event

Serious Adverse Events and adverse events that meet "severe" criteria must be directly reported within 24 hours to, the Principal Investigator and the IRB.

[name] M.D.
[contact]

[contact]
Department of Anesthesiology
Midwestern Regional Medical Center
Zion, IL

Other adverse events must be entered within 7 days of collection into the Oncore ERM.

F3 Study Outcome Measurements and Ascertainment

G Statistical Plan

Interim Monitoring and Early Stopping

The Principal Investigator will utilize the Oncore ERM study management system to monitor the study.

The study may be stopped early for the following reasons:

- withdrawal of funding
- safety issues
- drug has been proven effective and no further testing is needed

Analysis Plan

The study is a prospective, randomized, open, active controlled clinical trial. Effectiveness of the Continuous TAP (CTAP) via the ON-Q[®] Pain Management System will be evaluated and compared to single shot techniques with respect to reductions in postoperative opioid consumption over the first 72 hours postoperatively. Secondary outcomes including hospital length of stay (LOS), time in PACU, pain at rest and with activity, return of bowel function, and incidence of opioid related side effects will also be evaluated.

The aims of this study are to compare the efficacy of continuous TAP block via ON-Q[®] system versus that of single injection techniques for TAP block regarding opioid reduction among patients undergoing major abdominal surgery. It is hypothesized that a continuous TAP block technique reduces pain, the need for opioids as well as the expected length of stay relative to those resulting from those subjects receiving a single TAP injection of Exparel (liposomal Bupivacaine) or single TAP injection of Ropivacaine to treat postoperative pain.

Study success criteria:

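### The primary comparison, the time window and the success rule contradict each other, and the success rule omits the comparison on which the trial is sized

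*Combined protocol and SAP*

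**What the plan says.** The combined protocol and SAP states the main question in several places.

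- **Primary Hypothesis (Study Abstract).** Narcotic requirement over 48 hours, continuous-release methods against single-shot Bupivacaine.
- **Section C, Primary Aim.** The first comparison is of "total post-operative narcotic requirements (Dilaudid) required over 48 hrs. in the continuous catheter TAP block arm vs. the single shot Bupivacaine TAP arm". A second follows in the same sentence: Exparel against single-shot Bupivacaine. The Secondary Aim covers any "significant difference in narcotic requirements at other endpoints such as 24 hrs and at 72 hrs".
- **Section G, Analysis Plan.** The catheter technique is to be evaluated and "compared to single shot techniques with respect to reductions in postoperative opioid consumption over the first 72 hours postoperatively". Other outcomes are then called secondary.
- **Section G, Study success criteria.** Success means significantly lower opioid consumption with the catheter than in patients who "receive a single TAP injection of Exparel (liposomal bupivacaine) or single TAP injection of Ropivacaine to treat postoperative pain". The next sentence adds that finding no difference between catheter and Exparel would also be of benefit.
- **Section G, Sample Size.** "The main objective of study is to compare total opioid consumption between the single shot TAP group and the Exparel TAP group", and "A secondary aim is to examine a difference in mean opioid consumption between the single shot TAP group and continuous TAP group". No window is given.
- **Section G, Statistical Analysis Plan.** The same ranking is repeated, again without a window. A three-group ANOVA and a catheter versus Exparel test are added, with no stated order and no multiplicity rule.

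Two supporting details also disagree. Section B estimates 4.1 mg for single shot and 2.4 mg for the catheter at 48 hours and says of the third arm: "We would also assume Exparel TAP to be equal to catheter TAP at 2.4 mg". The Sample Size paragraph presents 2.4 mg (SD 1.3) as an Exparel result from previous studies and internal pilots. Sections D and E list the single-injection control as Bupivacaine, but the Analysis Plan and the success criteria call it Ropivacaine, and section E3.g describes floor staff as "blinded between the single injection arms: Exparel and Ropivacaine".

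**The concern.** Three things should be the same and are not: the stated primary aim, the comparison that is sized and analysed as primary, and the comparison that defines success. The success rule leaves out Exparel versus single shot and includes catheter versus Exparel, a difference that section B assumes to be zero. Its *or* can be read as beating either arm, both arms, or the two arms pooled.

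Because nothing sets precedence, the comparison, the window (48 or 72 hours) and the meaning of *or* could each be chosen after the data are seen, with protocol text to support the choice. The plan describes the trial as open, so a confirmatory claim would be hard to defend. The type I error rate is also undetermined: one primary test at 5% under the Sample Size and SAP text, two unadjusted tests under section C.

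**Working it through.** **Inputs.** Means: single shot 4.1 mg, catheter 2.4 mg, Exparel 2.4 mg (section B). SD 3 mg in all arms, the conservative value used for sizing; or 3 mg in control and 1.3 mg in the active arms (Sample Size; 1.3 applied to both). Two-sided 0.05, 80% power, 49 per arm, 53 recruited per arm with 10% dropout (Sample Size).

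**The plan's own figure.** n per arm = 2 × SD² × (z₀.₉₇₅ + z₀.₈₀)² / d² = 2 × 9 × 7.849 / 1.7² = 48.9, so 49. This reproduces (an exact t calculation gives 49.9, so 50). Evaluable number: 53 × 0.9 = 47.7, taken as 48 per arm.

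**The statements side by side.**

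| Place | Primary or lead comparison | Window |
|---|---|---|
| C, Primary Aim | Catheter vs single shot, and Exparel vs single shot | 48 h |
| G, Analysis Plan | Catheter vs single-shot techniques | 72 h |
| G, success criteria | Catheter vs Exparel *or* single-injection Ropivacaine | none |
| G, Sample Size and SAP | Exparel vs single shot only | none |

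**Chance of meeting the success sentence.** Simulation of 300,000 trials, normal data, 48 per arm, Welch t at two-sided 0.05, catheter significantly lower, with the arm called Ropivacaine taken to be the single-shot control:

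| Reading of *or* | SD 3 in all arms | SDs 3 / 1.3 / 1.3 |
|---|---|---|
| Either | 78% | 94% |
| Pooled | about 34% | 78% |
| Both | 2.5% | 2.5% |

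The last row follows directly. With equal true means, the chance that the catheter is significantly lower than Exparel is half of 0.05, and requiring a win over control as well barely changes it.

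**How often the SAP primary and the success rule disagree.** On the *either* reading, about 24% of trials with SD 3 (about 12% in each direction) and about 5% with SDs 3 / 1.3 / 1.3. On the *both* reading with SD 3, the SAP primary is met and the success rule fails in about 78%.

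**Familywise error if both section C comparisons are primary at 0.05.** The two tests share a control, so with equal SDs and equal arms their correlation is 0.5. The bivariate normal gives P(|Z₁| > 1.96 or |Z₂| > 1.96) = 0.0907. Simulated t-tests at n = 48 give 0.090 with SD 3 and 0.075 with SDs 3 / 1.3 / 1.3. Under the Sample Size and SAP text alone it is 0.05.

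**Power for the remedies, 48 per arm.**

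- One comparison with control at 0.05: with SD 3 the noncentrality is 1.7 / (3 × √(2/48)) = 2.78, power 78%. With SDs 3 and 1.3 it is 1.7 / √((9 + 1.69)/48) = 3.60, power 94%.
- One comparison at 0.025: 69% and 90%.
- Both control comparisons significant at 0.05: 67% and 92%.

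**The case against.** The best defence is that the Sample Size and Statistical Analysis Plan paragraphs agree with each other and could be taken to govern, leaving one primary test at 5%. The window is also less open than it looks: the Primary Hypothesis, the Primary Aim and the source of the 4.1 and 2.4 mg figures all say 48 hours, and only the Analysis Plan says 72. Ropivacaine as a single injection may be a naming slip, since every arm description says Bupivacaine. Section B gives the catheter the same assumed effect, so 49 per arm serves either control comparison at 0.05. Internal pilots may have supplied Exparel data. The sentence welcoming no difference between catheter and Exparel makes the *both* reading less natural. Whether two treatments against a shared control need adjustment is partly convention.

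Much of this stands as context. The sizing is not wrong for either comparison at 0.05, the 9% is conditional on section C governing, and the 2.5% is the extreme reading. The defence does not remove the conflict. The success rule sits in the same section G as the SAP and contradicts its ranking, and the SAP gives no window that would overrule the 72 hours stated a few paragraphs earlier. The sentence on no difference opens as a contrast and calls that result also beneficial, so it does not exclude the *both* reading. Even on the lenient reading, the two rules disagree in about 24% of trials with SD 3.

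**Conclusion.** The concern holds, and it must be fixed before analysis. The plan has three versions of its main comparison, two windows, and a success rule that can reach the opposite conclusion from the primary analysis, with no order of precedence. On the plan's own assumptions, the chance of declaring success runs from 2.5% to 78% with SD 3 mg (to 94% with SD 1.3 mg in the active arms), depending on the reading of one word. The error rate is 5% or about 9% (7.5% with the unequal SDs), depending on which section governs.

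These figures assume normal data, 48 evaluable per arm, and the single-shot arm as the control in the success rule. Opioid totals with mean 4.1 and SD 3 mg are probably skewed, so the percentages illustrate scale. The textual conflict does not depend on them.

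**What to change.** Put one statement, identically, in the Primary Aim, Analysis Plan, Study success criteria, Sample Size and Statistical Analysis Plan:

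1. Primary endpoint: total opioid consumption over 0–48 hours, the window behind the 4.1 versus 2.4 mg estimate.
2. Test Exparel versus the single-shot control first at two-sided 0.05, following the ranking already in the Sample Size and SAP text.
3. Test catheter versus the single-shot control at two-sided 0.05 only if the first test is significant. This holds the familywise error of the two tests at 5%.
4. Catheter versus Exparel, the three-group ANOVA, and the 24- and 72-hour totals are secondary.
5. Rewrite the success sentence to follow steps 1 to 3.
6. Reconcile the name of the control-arm drug (Bupivacaine or Ropivacaine) across the sections, and state whether the 2.4 mg figure comes from catheter or Exparel data.

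The cost is wording only, with no extra patients. The drawback is that the catheter claim depends on the Exparel result: both succeed in 67% of trials with SD 3, or 92% with SD 1.3 in the active arms. If the sponsor prefers to keep both section C comparisons co-primary, testing each at 0.025 gives 69% or 90% power per comparison, against 78% or 94% at 0.05.
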